10.4.3 Baseline descriptive statistics

Baseline characteristics will be summarized within each cohort using descriptive statistics. For categorical variables, frequencies and percentages will be presented. For continuous variables, the median and range will be presented. Inferential tests will not be performed.

10.4.4 Planned interim analyses (if applicable)

N/A

10.4.5 Analysis of influenza response and disease status endpoints

HAI will first be measured and summarized with mean and standard deviation at different time-points, respectively. Paired t-test will be further used to test whether there is significant change in HAI at different time points from baseline, respectively. Two sample t-test will be used to compare the change in HAI from baseline between two groups, at different time-point, respectively. Chi-Square test will be used to compare the Seroconversion and Seroprotection between two groups, respectively. Logistic regression model will be used to compare adjusted difference in Seroconversion and Seroprotection between two groups after adjusting for other factors, respectively.

Spearman/Pearson correlation coefficient will be used to measure the relationship between correlation between HAI, predefined risk of influenza-like illness (low, moderate, high), respectively. Finally Mixed model will be employed to test their correlations over the whole period with and without

adjusting for other factors, respectively. Kaplan Meir method, Log-rank test, and Cox model will be used to test the relationship between peak HAI and PFS.

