1. PRIMARY HYPOTHESES, OBJECTIVES, AND ENDPOINTS

Clinical		
Hypothesis	Objective	Endpoint
Continuous FluZone HD throughout the flu season will improve hemagglutination inhibition (HAI > 40) as measured at the end of the season compared to those patients that receive FluZone HD once.	Demonstrate an absolute 25% increase in seroprotection, defined as HAI>40 against all strains, at week 21 in the experimental arm compared to the control arm.	HAI will be measured in all patients at baseline, week 5, and week 21 to calculate seroconversion at week 5 and seroprotection at week 21. Seroconversion: Pre-vaccination HAI<10 and a post-vaccination HAI>40 or a pre-vaccination HAI >10 and a \geq 4-fold rise in post-vaccination HAI at week 5.

The above measurables will appear in the results section of www.clinicaltrials.gov at trial completion

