3.3 Influenza vaccination research in allogeneic transplant patients

An open-label randomized trial included 78 patients at least a week before a planned allogeneic stem cell transplant⁹. Odds ratio for all-cause mortality was 1.05 (95% CI 0.4 to 2.77) among those vaccinated. Influenza-related mortality was similar as well between the groups (2/40 among vaccinated versus 2/38 among non-vaccinated). Documented influenza infection rate was similar in vaccinated and unvaccinated patients (3/40 versus 4/38, respectively). GMTs at 30 days post-vaccination among the vaccinated population were significantly higher for influenza A/H1N1 and influenza A/H3N2 strains (15 versus 10, p=0.03 and 30 versus 12.5, p< 0.001, respectively).

Another open-label randomized trial enrolled 73 adults after allogeneic HSCT, of which 35 were randomized to receive an adjuvanted influenza vaccine (Fluad) and the rest (38) randomized to a non-adjuvanted influenza vaccine (Influvac)¹⁰. There were five cases (14%) of laboratory-confirmed influenza among patients receiving the adjuvanted vaccine compared to three cases (8%) in the non-adjuvanted vaccine group. Vaccine immunogenicity, reported as seroconversion rate, seroprotection rate, and GMTs, was not significantly higher in the adjuvanted vaccine group. This study was underpowered for conclusions regarding seroprotection or to identify differences in influenza-like illness between the groups.

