3.6 Assessment of influenza vaccination response

Influenza vaccines work by activating antigen-specific B-cells to proliferate and differentiate into plasmablasts that secrete protective antibodies and memory B cells that can rapidly proliferate and differentiate into plasmablasts upon re-encountering the immunizing antigen. Studies in healthy individuals demonstrated a transient plasmablast response after vaccination peaking at around 7 days after vaccination at which point it makes up to 16% of all B-cell, and returning to baseline levels by day 14. Memory B-cell response, on the other hand, peaks at 14-28 days after vaccination followed by a slower rate of decline²⁹⁻³¹. A subset of the plasmablasts migrate to the bone marrow and become long-lived plasma cells secreting antigen-specific antibodies for protracted periods of time. Memory B-cell and plasma cells provide a remarkably stable immunological memory that can persist over 50 years after vaccination in humans. Interestingly, plasma cells are not intrinsically long-lived and only a finite number of plasma cells survive after an immune response irrespective of the number of plasma cells generated, suggesting that plasma cells require a specialized niche for survival³². It remains unclear what factors direct the differentiation of activated, antigen-specific B-cells into either memory B-cells or plasmablasts and plasma cells. Studies in mice suggested that the B-cell repertoire in the memory B-cell and the plasma cells compartments differ in terms of antigen-binding affinity and breadth³³.

Generation of immunological memory is the hallmark of adaptive immune responses. Clinically, this can be measured by determining seroprotection, defined as the percentage of subjects with a post-vaccination hemagglutination antibody inhibition (HAI) titer $> 1:40$; and seroconversion, the percentage of subjects with either a pre-vaccination HAI titer $< 1:10$ and a post-vaccination HAI titer $> 1:40$ or a pre-vaccination HAI titer $> 1:10$ and a minimum four-fold rise in post-vaccination HAI antibody titer by week 5.

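### The supportive HAI analyses in 10.4.5 use means, SDs and t-tests of untransformed titres, although the protocol treats HAI as a ratio scale; log2 titres and GMTs would serve better

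*Combined protocol and SAP*

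**What the plan says.** Section 10.4.5 sets out the analysis of HAI as a continuous quantity in three steps. The summary is "HAI will first be measured and summarized with mean and standard deviation at different time-points, respectively". Within arms, "Paired t-test will be further used to test whether there is significant change in HAI at different time points from baseline, respectively". Between arms, "Two sample t-test will be used to compare the change in HAI from baseline between two groups, at different time-point, respectively". No logarithm, GMT, fold-rise summary or rank test between arms is named for these analyses, and no value is assigned to titres below 10. The same section goes on to correlation coefficients (Spearman or Pearson), a mixed model, and Kaplan-Meier, log-rank and Cox analyses of peak HAI against PFS.

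The binary endpoints are handled separately: "Chi-Square test will be used to compare the Seroconversion and Seroprotection between two groups, respectively", with logistic regression for the adjusted comparison. The primary objective in section 1 and the sample size in section 10.3 rest on binary seroprotection at week 21.

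Elsewhere the protocol treats titres as ratios. Section 3.6 gives titres as 1:10 and 1:40 and requires, for patients with a measurable starting titre, a "minimum four-fold rise in post-vaccination HAI antibody titer by week 5". Section 3.3 reports a cited trial in geometric means: "GMTs at 30 days post-vaccination among the vaccinated population were significantly higher". Section 10.4.3 uses median and range, not mean and SD, for continuous baseline variables.

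**The concern.** The planned t-tests score a response by the difference between two titres, whereas the protocol's own definition of response scores it by their ratio. The two can disagree sharply. A patient who goes from 640 to 1280 has only doubled and does not seroconvert, but contributes +640. A patient who goes from 20 to 80 has a four-fold rise and does seroconvert, but contributes +60. On the log2 scale the contributions are +1 and +2, in the order that the response definition implies.

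Titres are usually right-skewed. If these are, the arithmetic mean and SD will be set largely by a few patients, and the between-arm t-test will be less sensitive than it need be. This is the only specified direct comparison of the arms on the titre scale. A weak result there could appear to conflict with a positive seroprotection result merely because of the scale. Section 3.7 and the account of the earlier trials in section 3.5 show that the immunological result is meant to inform practice, so the supportive analysis should be read easily alongside the primary one.

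**Working it through.** **1. The plan's own figure, to see what depends on the scale.** From section 10.3: rates P1 = 0.333 and P2 = 0.585, equal arms (B = 0.5), alpha 0.05 (taken as two-sided), power 80%, R-squared 0.1. The mean rate is 0.459. For logistic regression on a binary covariate,

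n = [z(0.975)·√(0.459 × 0.541 / 0.5) + z(0.80)·√(0.333 × 0.667 + 0.585 × 0.415)]² / [(0.252)² × 0.5]
= (1.381 + 0.574)² / 0.03175 = 120.4.

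Dividing by 1 − 0.1 gives 133.8, so 134 as stated. The odds ratio is (0.585/0.415)/(0.333/0.667) = 2.82, also as stated. Only proportions enter, so the titre scale has no bearing on this number.

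**2. Leverage of a few titres (invented data).** Take 67 titres: 20 at 5, 12 at 10, 13 at 20, 10 at 40, 6 at 80, 3 at 160, and one each at 320, 640 and 1280. So 22/67 = 33% are at or above 40. The sum is 4080, so the mean is 60.9; the SD is 175.8 and the GMT 18.8. Without the three highest, the sum is 1840, so the mean is 28.8; the SD is 36.8 and the GMT 15.9. Three patients more than double the mean and raise the GMT by 18.8/15.9 − 1 = 18%.

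**3. Power of the planned between-arm t-test on change.** Assumptions, none of them given in the documents:
- log-normal titres for one strain, recorded on a two-fold grid, with titres below 10 set to 5;
- 67 per arm, with 33.3% v 58.5% at or above 40 at week 21;
- between-patient SD s in log2 units, the same at both visits;
- a modest control-arm rise from baseline. With a rise of 0.5 log2 units, a re-run agrees with each entry below to within 3 percentage points.

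| log2 SD | correlation 0.3, raw v log2 | correlation 0.5, raw v log2 | correlation 0.7, raw v log2 |
|---|---|---|---|
| 1.0 | 87% v 86% | 92% v 94% | 97% v 99% |
| 1.5 | 76% v 88% | 84% v 96% | 90% v over 99% |
| 2.0 | 62% v 89% | 70% v 95% | 78% v over 99% |
| 2.5 | 49% v 88% | 52% v 96% | 65% v over 99% |

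The log2 entries can be checked by hand. The arms differ by z(0.585) − z(0.333) = 0.215 + 0.432 = 0.646 SDs. The SD of change is s·√(2(1 − r)), so at r = 0.5 the standardised difference is 0.646. The noncentrality is 0.646 × √(67/2) = 3.74, and power is about Φ(3.74 − 1.96) = 96%. At r = 0.3 it is 0.646/√1.4 = 0.546, then 3.16 and 88%. The spread s cancels on the log2 scale. It does not cancel on the raw scale, which is why only the raw entries fall as s grows.

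**4. Summary statistics under the same model.** In the experimental arm at week 21, the arithmetic mean is about 1.3, 1.7, 2.4 and 3.6 times the geometric mean at log2 SD 1.0, 1.5, 2.0 and 2.5. The three highest of 67 titres make up about 15%, 23%, 32% and 42% of the total.

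**5. Type I error.** With no arm difference (correlation 0.6), the nominal 5% test rejects in 4.5%, 5.1%, 4.3% and 2.6% of trials on raw titres and in 5.2%, 5.3%, 4.5% and 4.5% on log2 titres. The raw test is not anticonservative.

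**The case against.** The strongest reply is that nothing decisive depends on this. The trial's conclusion rests on a threshold endpoint tested by chi-square and logistic regression, and seroconversion depends on thresholds and fold rise. That is correct, and it sets the limit of the point. A reader might infer that the main between-arm comparison or the false-positive rate is compromised; steps 1 and 5 show that neither is.

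A reader might also infer that the t-test on change is the only planned use of the full titre scale. It is not, since 10.4.5 also plans correlations, a mixed model and a Cox model of peak HAI.

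The size of the loss is also open to challenge. The documents give neither an SD nor a correlation, and a log-normal model favours the log2 test by construction. At a log2 SD of 1.0 there is almost nothing to gain, and at correlation 0.3 the raw test does as well. This stands: a large loss is possible, not established.

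Further, 33.3% and 58.5% are the design rates for protection against all strains, and rates for a single strain cannot be lower than these. The simulation borrows them for one strain. Moving every log2 titre by the same amount only multiplies raw titres by a constant, which changes neither test apart from the floor at 5. The same holds for reading the threshold as above 40 or as 40 and above. A different gap between the arms would change both power figures, so the table is an illustration and not a forecast.

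Finally, the documents do not use the terms raw scale or two-fold dilution series. The first follows from naming means and t-tests without a transformation; the second is a reading of the titres 1:10 and 1:40 and the four-fold rule. The GMTs in section 3.3 are background from a transplant trial and not this trial's benchmark, so comparability with them is a minor gain.

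**Conclusion.** The point holds for the supportive continuous HAI analyses only. As written, 10.4.5 analyses a ratio-scale measurement by differences, against the protocol's own four-fold definition of response. The consequence is a summary that a few patients can dominate and a between-arm test that may be less powerful than the same test on log2 titres. In the illustration the difference in power runs from nil at a log2 SD of 1.0 to roughly 35 to 45 percentage points at 2.5, under assumed log-normal titres, correlations of 0.3 to 0.7 and single-strain rates of 33.3% and 58.5%. The direction is secure if titres are skewed; the size cannot be fixed from the documents. The documents do not support reading this as a flaw in the primary comparison, the seroconversion comparison, the sample size of 134 or control of type I error. It should be changed because the better method is standard and costs almost nothing.

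**What to change.** In section 10.4.5:
- replace the mean and SD of HAI with the GMT and 95% CI by arm, strain and time point;
- run the paired and two-sample t-tests on log2 titres, and state the value given to titres below 10 (for example 5);
- report the geometric mean fold rise from baseline, and its between-arm ratio, with 95% CI by strain;
- use log2 titres in the Pearson correlation, the mixed model and the Cox model. Spearman is unchanged by the transformation.

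Reporting by strain also settles which titre the single term HAI means in these analyses. The plan does not say, although section 7.1 lists three vaccine strains for 2019-2020 and four for 2020-2021.

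The cost is a wording change made before the analysis. It needs no new data or patients, and the primary analysis and the sample size stay as they are.

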TITLE: INFLUENZA VACCINATION IN PLASMA CELL DYSCRASIAS

Coordinating Center: Winship Cancer Institute of Emory University

Winship PI: [name] MD MPH

Laboratory investigator: [name] MBBS

Sanofi: Fluzone HD

Commercial Agent: Prevnar 13 (PCV 13)

Statistician: [name] Winship BBISR

Protocol / Date:

Initial / 7-May-2019
V 1.1 / 22-May-2019
V 1.2 / 13-Jul-2019
V 1.3 / 31-Oct-2019
V 1.31 / 13-Nov-2019
V 2.0 / 9-Mar-2020
V 2.1 / 7-Apr-2020
V 2.2 / 3-Jul-2020
V 2.3 / 20-Jul-2020
V 2.4 / 14-Sep-2020

CTCAE version: 5.0

[figure not shown]
Total consented patients: 175 total
50 patients (2019-2020) of which 23 were evaluable
125 patients (2020-2021)

Text color legend

Blue text
Blue text

Instructions and detailed for correlative science for laboratory #1
Instructions and detailed for correlative science for laboratory #2

SCHEMA

This is a phase IV randomized trial of 148 evaluable patients with a plasma cell disorder to be enrolled as early as possible in the influenza season through 15-Dec.

Fluzone HD refers to TIV formulation for 2019-2020 influenza season and QIV formulation for 2020-2021 season.

After eligibility is confirmed, patients will be randomized 1:1 to either an experimental arm where each patient receives three injections of Fluzone HD and a control arm where each patient receives one injection of Fluzone HD.

All patients receive Prevnar at week 5 if they have not received either PCV13 or PPSV23 in that calendar year.

STANDARD OF CARE AND RESEARCH INTERVENTIONS

Timing	Week 1	Week 5	Week 9	Week 17	Week 21
Standard of care tests	
 Blood tests Clinic visit 	Prevnar (PCV13)			Myeloma proteins
Research	
 Consent Eligibility Research blood Fluzone HD #1 	Research blood	Fluzone HD #2	Fluzone HD #3	Research blood

Timing	Week 1	Week 5	Week 9	Week 17	Week 21
Standard of care tests	
 Blood tests Clinic visit 	Prevnar (PCV13)			Myeloma proteins
Research	
 Consent Eligibility Research blood Fluzone HD #1 	Research blood			Research blood

Table of Contents

1. PRIMARY HYPOTHESES, OBJECTIVES, AND ENDPOINTS	6
2. EXPLORATORY SCIENTIFIC HYPOTHESES, OBJECTIVES, AND ENDPOINTS	6
3. BACKGROUND	6
3.1 INFLUENZA OVERVIEW	6
3.2 INFLUENZA RISK IN ADULT CANCER PATIENTS	6
3.3 INFLUENZA VACCINATION RESEARCH IN ALLOGENEIC TRANSPLANT PATIENTS.....	7
3.4 MULTIPLE MYELOMA.....	7
3.5 MYELOMA PATIENTS AND INFLUENZA.....	8

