10.3 Sample size determination

In the initial design, the sample sizes of 81 in each group achieved 90% power to detect a difference between the group proportions of 0.2520. The proportion in group one (the intense Fluzone HD arm) is assumed to be 0.3330 under the null hypothesis and 0.5850 under the alternative hypothesis. The proportion in group two (the control group) is 0.3330. The test statistic used is the two-sided Z test with pooled variance. The significance level of the test (the alpha) was targeted at 0.0500, i.e. the probability of rejecting a true null hypothesis that was desired. The significance level

actually achieved by this design is 0.0513. The planned power was 0.9, i.e. the probability of rejecting a false null hypothesis. We assume 10% drop off rate in the study so that we planned to enroll 90 patients in each group.

During the first influenza season (2019-2020), we enrolled 50 patients of which only 23 were evaluable as 27 patients missed the week 21 study assessment due to COVID19.

We aim to complete the trial during the influenza season 2020-2021, and hence will need to control season as a confounder through a logistic regression model. A logistic regression of a binary response variable (e.g. HAI>40) on a binary independent variable (e.g. the treatment arms) with a sample size of 134 observations (of which the two treatment arms are evenly distributed) achieves 80% power at a 0.05 significance level to detect a change in the rate of HAI>40 from the baseline value of 0.333 to 0.585. This change corresponds to an odds ratio of 2.82. An adjustment was made since a multiple regression of the independent variable of interest on the other independent variables (e.g. the seasons) in the logistic regression obtained an R-Squared of 0.1. Hence we will need 67 patients in each randomized arm. After taking into account the expected 10% dropout rate, we plan to enroll 74 patients in each arm, producing a total sample size of 148 patients. Given we already accrued 11 evaluable patients per arm during the first season, we will plan to enroll an additional 125 patients in the second season.

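### Section 10.4.5 should name the season-adjusted logistic regression as the primary test of week-21 seroprotection, close its covariate list, and add baseline HAI

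*Combined protocol and SAP*

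**What the plan says.** Section 10.3 describes two designs. For the initial one, with 81 per arm, "The test statistic used is the two-sided Z test with pooled variance". After the first season yielded only 23 evaluable patients, the trial was extended to a second season. The plan says it "hence will need to control season as a confounder through a logistic regression model" and derives 134 evaluable patients (67 per arm, 148 enrolled) from that model. Season appears there only as an example of the other independent variables.

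Section 10.4.5, the analysis section, gives two methods for the same endpoint. The first is "Chi-Square test will be used to compare the Seroconversion and Seroprotection between two groups, respectively". The second is "Logistic regression model will be used to compare adjusted difference in Seroconversion and Seroprotection between two groups after adjusting for other factors, respectively". Neither is labelled primary, season is not mentioned and no covariate is listed.

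The objective in Section 1 is "Demonstrate an absolute 25% increase in seroprotection, defined as HAI>40 against all strains, at week 21". The same section says "HAI will be measured in all patients at baseline, week 5, and week 21". In 10.4.5, baseline HAI enters the arm comparison only through t-tests on change. The scale of those tests (raw or log titre) is not stated.

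**The concern.** The model that justifies the sample size should be the model whose p-value is reported. As 10.4.5 stands, an analyst could report the chi-square, a season-adjusted model, or a model with any other covariates, and comply with the plan.

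Season has a specific reason to be in the model. The Schema says "Fluzone HD refers to TIV formulation for 2019-2020 influenza season and QIV formulation for 2020-2021 season", so the all-strain endpoint requires three strains in one season and four in the other. The same per-strain response then gives a lower all-strain rate in the second season.

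A covariate picked after results are seen could move the trial's main p-value. In addition, a potentially strong predictor of week-21 titre, which the plan already collects, is left out of the main comparison.

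**Working it through.** **1. Reproduce the plan's figures.** Inputs from 10.3: rates 0.333 and 0.585, equal arms, 80% power, alpha 0.05 (taken as two-sided), R-squared 0.1 between arm and the other covariates.

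- Odds ratio: (0.585/0.415)/(0.333/0.667) = 2.82, as stated.
- Logistic regression with a binary covariate, B = 0.5, mean rate 0.459: N = [1.960 × √(0.459×0.541/0.5) + 0.842 × √(0.333×0.667 + 0.585×0.415)]² / (0.252² × 0.5) = (1.381 + 0.574)² / 0.03175 = 120.4.
- After R-squared: 120.4/(1 − 0.1) = 133.8, so 134, as stated.
- Dropout: 67/0.9 = 74.4; the plan has 74 per arm.
- Initial design, exact enumeration of the pooled Z test at 81 per arm: size 0.0513 and power 0.901, both as stated.

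By the same formula, power at 134 is 80.1% with R-squared 0.1 and 84.1% with R-squared 0. Balanced 1:1 allocation within season puts R-squared near 0, which is why simulated power exceeds 80%.

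**2. Does the choice of test matter?** Simulation: 67 per arm (11 in season 1 with three strains, 56 in season 2 with four), all-strain rates held at 33.3% and 58.5%, 4000 trials per setting. The documents give neither the between-strain correlation (rs) nor r, so both are assumed. The covariate is mean baseline log2 HAI over that season's strains. Power:

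| rs | r | Chi-square | Season only | Season + baseline | Gain over season only (points) |
|---|---|---|---|---|---|
| 0.3 | 0 | 82.6% | 82.9% | 83.8% | 0.9 |
| 0.3 | 0.3 | 82.9% | 83.1% | 85.5% | 2.4 |
| 0.3 | 0.5 | 83.7% | 83.9% | 88.6% | 4.7 |
| 0.3 | 0.7 | 84.1% | 84.4% | 92.4% | 8.0 |
| 0.6 | 0 | 82.3% | 82.5% | 83.4% | 0.9 |
| 0.6 | 0.3 | 83.0% | 83.3% | 85.8% | 2.5 |
| 0.6 | 0.5 | 82.5% | 82.8% | 88.2% | 5.4 |
| 0.6 | 0.7 | 82.9% | 83.2% | 94.0% | 10.8 |

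The first two tests are practically the same. With equal per-strain response, a 33.3% three-strain rate becomes 26.1% (rs = 0.3) or 28.4% (rs = 0.6) with four strains. Even then, chi-square and season-only power differ by at most 0.5 points.

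**3. Weaker r in the arm re-vaccinated at weeks 9 and 17** (season only to season + baseline; rs = 0.3, then 0.6):

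- r 0.5 control, 0.2 experimental: 83.2 to 86.3%; 82.8 to 86.0%.
- r 0.7 and 0.3: 83.1 to 88.6%; 83.1 to 89.2%.
- r 0.5 and 0: 83.6 to 85.6%; 83.5 to 85.6%.

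The gain is about 2-6 points.

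**4. Type I error.** Single tests: 4.5-6.0%. Better of chi-square and season-only: 4.8-6.0%. Better of chi-square and baseline-adjusted (rs = 0.3, then 0.6): 5.7% and 6.4% at r = 0.3; 7.3% and 6.9% at r = 0.5; 7.5% and 8.1% at r = 0.7.

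**5. A second parameterisation**, by odds ratio per SD of baseline titre, agrees. Season + baseline power is 84, 86, 90, 94 and 96% at odds ratios 1.0, 1.65, 2.7, 4.5 and 7.4, with type I error 4.7-5.4% when that model is fixed in advance. The arm odds ratio becomes conditional: the marginal 2.82 corresponds to about 3.0, 3.5 and 4.3 at 1.65, 2.7 and 4.5.

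**The case against.** The best defence is that 10.3 sits in the same chapter and states the intention to adjust for season. The logistic model in 10.4.5 can be read as that model, with season among its unnamed factors. That is fair: the season part is a cross-reference gap, and by the figures above it has almost no numerical effect. What remains is that 10.4.5 offers two unranked tests and leaves the covariates open.

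The type I warning is conditional. No section proposes choosing a baseline-adjusted model after the fact, and at r = 0.3 the excess is barely above the single-test range.

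Omitting an optional covariate from a design that meets its planned power is not an error. Every gain quoted rests on correlations that the documents do not give. The apparent gain at r = 0 is slight test liberality, not information: with a pure-noise covariate, power moved from 83.6% to 84.0%, while null rejection rose from 5.55% to 5.71% (rate 0.333) and from 4.8% to 5.3% (rate 0.459). Part of the gain at r = 0.3 is the same effect.

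A reader might also infer that the HAI t-tests lose substantial power on raw titres. The documents do not support this: 10.4.5 never says the titres are raw, and no titre SD is given. Nor can an effect size be taken by converting 33.3% and 58.5% as if for one strain (0.646 SD), because the all-strain endpoint implies about 0.51-0.59 SD per strain. No power figure is offered for those analyses.

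**Conclusion.** The point stands as a gap in specification plus a free improvement. The plan's sample size reproduces, and power is adequate with either listed test. A reader might conclude that the trial is mis-sized or underpowered, or that switching between the chi-square and the season model inflates error. Neither follows.

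The exposure is the open covariate list: about 6% type I error at r = 0.3 and 7-8% at r = 0.5-0.7, and only if a baseline-adjusted model can be selected after the data are seen. Fixing season plus baseline HAI in advance holds type I error near 5%. It adds about 0-1, 2-3, 5-6 or 8-11 points of power at r = 0, 0.3, 0.5 or 0.7, and about 2-6 points if r is weaker in the experimental arm. These gains rest on assumed r, between-strain correlation and exchangeable strains. The direction is safe, because an uninformative baseline costs no power; the size is uncertain.

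**What to change.** In 10.4.5:

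- Name one primary test for week-21 seroprotection: logistic regression on arm with season and baseline log2 HAI. Fix the form of the covariate before HAI results are read, for example the mean over that season's vaccine strains.
- Close the covariate list and make the chi-square supportive.
- Report a standardised risk difference with 95% CI. The objective is an absolute difference of 25 points, and the adjusted odds ratio is conditional, so it is not comparable with the planned 2.82.
- For the supporting HAI analyses, state the log2 scale. Report geometric mean titre and geometric mean fold-rise per strain with 95% CI, and compare arms by ANCOVA with baseline log2 titre and season.

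If baseline HAI is not adopted, the minimum is to name the season-adjusted model from 10.3 as primary and close the list.

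Cost: SAP wording, a rule for summarising three or four baseline titres, and minor programming. No new data, visits or patients are needed, and the 134 evaluable patients are unchanged, since the R-squared term in the plan's formula reflects only correlation between arm and covariates.
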